2. Cirrhosis or advanced bridging fibrosis wherein the subject has greater than 5 years of obesity (body mass index [BMI] >30) and/or diabetes with negative viral hepatitis markers and a biopsy showing cirrhosis or advanced bridging fibrosis with any amount of fat

Subjects who meet all of the inclusion criteria and none of the exclusion criteria will proceed to randomization and the treatment phase. Subjects who fail to meet eligibility criteria due to an abnormal laboratory result may undergo retesting of the abnormal laboratory parameter during the screening window and at the discretion of the investigator and with prior approval of the medical monitor.

**Treatment Phase:** Subjects with portal hypertension who meet all of the other criteria for study inclusion will be randomly assigned (1:1:1) to receive 1 of 3 treatment assignments including placebo, GR-MD-02 in a dose of 2 mg/kg lean body mass, or GR-MD-02 in a dose of 8 mg/kg lean body mass administered every other week over a 52-week period for a total of 26 infusions. During the treatment phase of the study, all subjects randomly assigned to IMP will attend study visits according to the schedule of visits for study administration and monitoring (Table 12-2). Safety (12-lead electrocardiogram [ECG], physical examinations, vital sign measurements, adverse event [AE] monitoring, and safety laboratory assessments), and efficacy (FibroScan, MBT (if available), biomarkers, assessment of cirrhosis complications [esophageal variceal hemorrhage or portal hypertensive gastropathy

hemorrhage, clinically apparent ascites, spontaneous bacterial peritonitis, overt hepatic encephalopathy, listing for a liver transplant or the performance of a liver transplant], and quality of life) will be monitored throughout the treatment phase.

**Postdose Final Visit (14-28 days):** All subjects will attend a visit (or visits) 14 to 28 days after final dose. During this visit, safety (AE monitoring and safety laboratory assessments) and efficacy (FibroScan, MBT [if available], biomarkers, EGD, HVPG, and a liver biopsy) assessments will be collected/performed ([Table 12-2](#)).

**Follow-up/Early Termination Visit:** All subjects are to attend a follow-up/early termination visit 14 days after the postdose final visit to evaluate safety. During this visit, a 12-lead ECG, a physical examination, vital sign measurements, and AE monitoring will be collected/performed ([Table 12-2](#)).

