## **4.2.2 Handling of Withdrawals**

Subjects are free to withdraw from the study or study treatment at any time upon request. Subject participation in the study may be stopped at any time at the discretion of the investigator or at the request of the sponsor.

Subjects who discontinue study treatment or active participation in the study will no longer receive IMP. When a subject withdraws from the study, the reason(s) for withdrawal shall be recorded by the investigator on the relevant page of the electronic case report form (eCRF). Whenever possible, all subjects who discontinue study treatment or withdraw from the study prematurely will undergo all end-of-study assessments. Subjects who fail to return for final assessments will be contacted by the study center (2 documented telephone calls followed by 1 registered letter) in an attempt to have them comply with the protocol.

It is vital to obtain follow-up data on any subject withdrawn because of an AE or serious AE (SAE). In every case, efforts must be made to undertake protocol-specified, safety, follow-up procedures.

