#### **6.1.3.4 Infusion Visits 2, 3, 4, 5, and 6 (Weeks 3, 5, 7, 9, and 11 $\pm$ 3 Days, respectively)**

The following procedures and assessments will be performed prior to administration of IMP:

- Enter the IWRS and register subject visit data.
- Alcohol TLFB (This will be given to the subject at the beginning of the visit and will be considered source documentation.) (Infusion Visit 5)
- Assessment of cirrhosis complications (Infusion Visits 3 and 5).
- Perform a limited physical examination (including weight and examination of the heart, lung, and abdomen).

- Collect vital sign measurements (including heart and respiratory rate, blood pressure, and body temperature).
- Perform urine pregnancy test (females of childbearing potential only) (Infusion Visits 3 and 5).

The following information will be collected after IMP administration:

- AE monitoring.
- Record concomitant medications.

The following will be performed 2 hours after the end of the IMP infusion

- Collect PK sample (Infusion Visits 2, 3, and 4)

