#### **6.1.4 Follow-up (14-28 Days After Final Dose; Weeks 53-55 $\pm$ 3 Days)**

Within 14 to 28 days after the final 26th dose of IMP or, where feasible, following study termination, the following information will be collected ([Table 12-2](#)):

- Enter the IWRS and register subject visit data
- Perform a limited physical examination including weight and examination of the heart, lung, and abdomen)
- Collect vital sign measurements (including heart and respiratory rate, blood pressure, and body temperature)

- Conduct a FibroScan
- Perform MBT (if available)
- Collect biomarkers blood sample (will include the ELF test, FibroTest [FibroSure], and galectin-3)
- Perform EGD (must be performed on a different day within the 14 to 28-day follow-up period than when the HVPG assessment is performed)
- Perform HVPG
- Obtain a liver biopsy
- Perform hematology testing
- Perform blood chemistry testing
- AE monitoring
- Record concomitant medications

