### **6.2.6 MELD Score**

The MELD score assesses the severity of chronic liver disease and is used for prioritizing allocation of liver transplants. The MELD score will be calculated from laboratory tests (serum bilirubin, serum creatinine, and prothrombin time INR).

MELD score =  $(0.957 \times \ln(\text{serum creatinine}) + 0.378 \times \ln(\text{serum bilirubin}) + 1.120 \times \ln(\text{INR}) + 0.643) \times 10$  (if hemodialysis, value for creatinine is automatically set to 4.0)

Note: If any score is less than 1, the MELD assumes the score is equal to 1.

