e Vital sign measurements include heart and respiratory rate, blood pressure and body temperature prior to IMP administration. Blood pressure will be obtained with the subject in the supine position and measured twice consecutively with a 1-minute interval between measurements. The average of the 2 measurements will be recorded.

- f Hematology will include complete blood cell count with differential (red blood cells, white blood cells, , red cell indices, platelets, hemoglobin, and hematocrit).
- g Blood chemistry will include alanine aminotransferase, aspartate aminotransferase, albumin, alkaline phosphatase, bicarbonate, blood urea nitrogen, calcium, chloride, creatinine, glucose, lactate dehydrogenase, magnesium, phosphorus, potassium, sodium, total and direct bilirubin, total protein, uric acid,  $\gamma$ -glutamyl transferase, and fasting insulin level. Subjects must be in a fasted state prior to blood collection.
- h Biomarker blood tests will include the enhanced liver fibrosis test, FibroTest (FibroSure), and galectin-3 and will occur prior to first infusion and at Infusion Visits 13 and 14 to 28 days following final 26th infusion.
- i IMP administration will occur after the following procedures: limited physical examination, vital sign measurements, hematology, blood chemistry, and biomarker blood samples.
- j Within 14 to 28 days after the final 26th dose of IMP or where feasible following study termination due to the occurrence of a clinical event or withdrawal of consent. EGD must be performed on a different day within the 14- to 28-day follow-up period than when the HVPG assessment is performed.
- k The PK sample will be collected 2 hours after the end of the IMP infusion.

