Follow-up/Early Termination Visit: All subjects are to attend a follow-up/early termination visit 14 days after the postdose final visit to evaluate safety. During this visit, safety assessments will be collected/performed. Whenever possible, all subjects who are terminated from the study early should have a FibroScan[®] and an MBT performed at a follow-up visit. Whenever possible, subjects who are terminated from the study following at least 13 infusions should also have all the post-study evaluations including EGD, HVPG, and liver biopsy performed in addition to the FibroScan[®] and MBT.

Open-Label Extension Study: Following study completion, subjects will be offered enrollment into a subsequent separate study, an open-label extension study (OLES), if there is adequate tolerability and no safety issues or signs of clinical progression that would require discontinuation.

End-of-Study Telephone Contact: Subjects who do not enroll into the OLES, will be contacted via phone every 6 months for 2 years, and annually thereafter for a total of 4 years, for a brief update and are to be assessed for survival, listing for liver transplantation, liver transplantation, or complications of chronic liver disease (ascites, spontaneous bacterial peritonitis, variceal bleeding, and encephalopathy).

Figure 3-1 Study Design GT-026

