3.2.5. PK Endpoint

The PK endpoints include plasma concentrations and population PK parameters of GR-MD-02.

The population PK analysis will be described in a separate modeling analysis plan.

4. General Statistical Considerations

Study day for events on or after the date of the first infusion will be defined as the number of days from the date of the first infusion of IMP, plus 1 day, so that the date of the first

infusion will be defined as Day 1. For events before the date of the first infusion, study day will be calculated as the difference in days between the date of the first infusion and the date of interest. Thus, the day before the date of the first infusion will be defined as Day -1. This means there will be no study day zero (0).

Baseline is defined as the last assessment prior to the first infusion of IMP. All baseline measurements must have been collected prior to administration of first infusion of IMP. Measurements that are obtained after the first infusion of IMP will be considered as post-baseline values. If the measurement of a variable is not made on a given subject prior to the first infusion of IMP, then that subject will be considered not to have a baseline value for that variable. Change from baseline is defined as post-baseline assessment minus baseline assessment.

Continuous data will be described using the following descriptive statistics: the number of subjects (n), mean, standard deviation (SD), median, the first quartile (Q1), the third quartile (Q3), minimum and maximum, where appropriate. Categorical data will be summarized using the frequency count (n) and percentage (%) of subjects for each category, where appropriate.

Unless otherwise specified, all statistical tests and confident intervals (CIs) will be two-sided and conducted at the 0.05 significance level. If analysis variables are not normally distributed, Poisson-regression model (or the negative binomial) will be applied for counts data.

No imputation will be applied for missing data unless otherwise specified.

All collected data used for safety and efficacy evaluations will be presented in listings. Data will be displayed in all listings sorted by treatment group and subject identifier unless specified otherwise.

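### No visit after discontinuation schedules Child-Turcotte-Pugh, MELD or the cirrhosis-complications assessment, so two components of a key secondary composite have no exit reading in early leavers

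*Protocol*

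**What the plan says.** The cirrhosis-progression endpoint (protocol 7.2; SAP 3.2.2 and 8.2) counts a subject who develops any of ten events. Two of them are score-based: a Child-Turcotte-Pugh rise of at least 2 points, and a MELD of 15 or more.

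Two visits follow treatment. Section 6.1.4 covers completers and, where it can be arranged, early leavers: "Within 14 to 28 days after the final 26th dose of IMP or, where feasible, following study termination, the following information will be collected". Two weeks later comes the Follow-up/Early Termination visit of 3.1 and 6.1.5: "During this visit, a 12-lead ECG, a physical examination, vital sign measurements, and AE monitoring will be collected/performed".

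On withdrawals, protocol 4.2.2 says: "Whenever possible, all subjects who discontinue study treatment or withdraw from the study prematurely will undergo all end-of-study assessments". It does not list those assessments. SAP 3.1 asks for FibroScan and MBT in all who are terminated early, and adds: "Whenever possible, subjects who are terminated from the study following at least 13 infusions should also have all the post-study evaluations", naming EGD, HVPG and biopsy.

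On analysis, SAP 8.2.1 compares the composite between groups with a chi-square test in the FAS. The general rule in SAP section 4 is: "No imputation will be applied for missing data unless otherwise specified".

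On INR, protocol 6.2.6 states: "The MELD score will be calculated from laboratory tests (serum bilirubin, serum creatinine, and prothrombin time INR"). Table 6-1 also scores INR for Child-Turcotte-Pugh. Footnote f of Table 12-2 reads: "Hematology will include complete blood cell count with differential", and its list contains no clotting test. Section 6.4.8 includes prothrombin time under hematology.

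**The concern.** A composite defined partly by scores can count an event only when the score is taken. If the scores are not scheduled at exit, a subject whose liver function has worsened since the last scored visit leaves with that worsening unrecorded. The SAP does not say whether such a subject counts as event-free in the FAS or is left out. If counted as event-free, any unrecorded event lowers the observed incidence. If left out, the result depends on whether leaving is related to progression. In either case a difference between arms in the number or timing of exits could distort the comparison.

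The protocol makes a link between leaving and worsening plausible. Section 4.2.1 lists clinically significant biochemical change among the reasons for withdrawal, and Table 12-2 footnote j foresees termination because of a clinical event.

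The INR passages are a separate matter. They affect whether the scores can be calculated at the visits where they are scheduled.

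**Working it through.** The plan gives no figure for this point, so the check is a reading of the schedule followed by a short count.

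**Step 1: what is scheduled, and when** (sections 6.1.3 to 6.1.5, Table 12-2).

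| Item | Infusion Visits | 14-28-day visit | Follow-up/Early Termination |
|---|---|---|---|
| Child-Turcotte-Pugh | 13, 26 | no | no |
| MELD | 13, 26 | no | no |
| Cirrhosis complications | 3, 5, 7, 9, 11, 13, 15, 17, 19, 21, 23, 25, 26 | no | no |
| Chemistry, hematology | 1, 7, 13, 20, 26 | yes | no |
| EGD | none | yes | no |
| CLDQ (exploratory) | 1, 26 | no | no |

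Complications are assessed at 13 visits, starting at Week 5 ("Assessment of cirrhosis complications (Infusion Visits 3 and 5" for the first block). The scores are taken twice after screening. A subject whose last infusion is Visit 25 (Week 49) leaves 49 − 25 = 24 weeks after the last scheduled score.

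**Step 2: which of the ten components lose their exit reading.** The two varices components are covered by EGD if the 6.1.4 visit takes place. Bleeding, ascites, peritonitis, encephalopathy, transplant and death can surface through adverse event reporting or the telephone contacts. The two score-based components have no scheduled exit source.

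The MELD component has a further difficulty. The objectives (protocol 2.2, SAP 2.2) require the threshold on two consecutive occasions, while the endpoint sections do not. A screening MELD of 15 or more is excluded, so someone who leaves between Visits 13 and 26 has one scheduled reading that could count. The two-occasion version cannot be met from scheduled visits.

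**Step 3: how many subjects.** Inputs: 156 randomized and 25% dropout (protocol 7.6), Visit 13 at Week 25, Visit 26 at Week 51. Assumption: all dropouts leave before Visit 26.

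- Early leavers: 0.25 × 156 = 39, or 0.25 × 52 = 13 per arm.
- Share leaving before Week 25 if exits are even over Weeks 1 to 51: (25 − 1)/(51 − 1) = 0.48.
- Early leavers with no scheduled post-baseline score: 0.48 × 39 = 18.7, about 19 (19/156 = 12% of the FAS).
- Range, taking 30% to 70% of exits before Week 25: 0.30 × 39 = 11.7, about 12 (8%), to 0.70 × 39 = 27.3, about 27 (17%).

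The documents give no timing of exits, so the range is an assumption.

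**Step 4: the analysis rules.** SAP 8.2.1 adds LOCF analyses for CPA, FibroScan and MBT but none for the composite. Its sensitivity analyses are the MITT and PP sets and a log-rank test, with event-free subjects censored at their last complications assessment (continuation of 8.2.1). An early leaver is therefore censored at an on-treatment visit. The SAP addendum's rules for filling in values belong to post hoc analyses.

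**Step 5: INR.** Against a post-screening INR: Table 12-1 has a coagulation row and Table 12-2 has none, and footnote f lists only the blood count. For it: section 6.4.8 puts prothrombin time under hematology, Table 12-2 orders MELD at Visits 13 and 26, and SAP 9.2 summarises coagulation at post-baseline visits. The passages conflict.

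**The case against.** The case for leaving the schedule alone has substance.

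- **Early leavers are not unobserved.** Complications are assessed from Week 5, and anyone who reaches Week 25 has both scores. This stands and confines the gap to the period after the last scored visit.
- **The 6.1.4 visit could supply much of what is missing.** It draws bilirubin, albumin and creatinine and includes an abdominal examination. If section 6.4.8 governs, it also gives prothrombin time, so MELD and the laboratory part of Child-Turcotte-Pugh could be derived. This stands in part: nothing instructs anyone to derive them, the visit is held only where feasible, and the Early Termination visit draws no blood.
- **Progression must be reported as an adverse event (6.4.5.3), and there are telephone contacts (6.1.6).** Neither yields a score. Section 6.4.7 exempts laboratory changes associated with the underlying disease unless they are worse than expected. The calls omit the scores, begin at Month 6, and cover only subjects who do not enter the extension study.
- **The composite is tested last:** fourth of four in protocol 7.9.2 and sixth of six in SAP 8.2.1. This limits the consequence, because any earlier failure makes the composite exploratory.

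A reader might infer three stronger things. One is that neither score can be calculated even in completers because no INR is drawn after screening. That follows only if footnote f overrides section 6.4.8, and the MELD row and SAP 9.2 point the other way. Another is that early leavers are the subjects most likely to have progressed, so that the result is biased in a known direction. The documents make a link possible but give no data on its frequency, and the withdrawal reasons also include noncompliance, pregnancy and withdrawn consent. The third is that the missing CLDQ weakens the composite. CLDQ is exploratory and not part of it.

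**Conclusion.** The point holds as an avoidable gap in data collection. The Child-Turcotte-Pugh and MELD components of a formally tested key secondary have no scheduled reading after discontinuation, and the prespecified analysis neither fills the gap nor says how such subjects are classified. About 39 of 156 subjects would be affected at the planned dropout. About 12 to 27 of them, 19 if exits are even, would have no scheduled post-baseline score at all.

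These counts rest on a dropout allowance made for the HVPG sample size, on all dropouts leaving before Visit 26, and on an assumed timing of exits. The size and direction of any bias cannot be estimated from the documents. The INR question is a contradiction to reconcile and does not show that the test is missing.

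The schedule checked is that of the protocol dated 20 February 2015. SAP 10.1 describes nondosing visits that this protocol lacks, so if a later schedule exists the same check should be made on it.

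**What to change.** 1. In section 6.1.4 and Table 12-2, for subjects who did not reach Infusion Visit 26, add Child-Turcotte-Pugh, MELD (with chemistry and PT/INR) and the cirrhosis-complications assessment. If the 6.1.4 visit did not take place, require the same items at the Early Termination visit in section 6.1.5.
2. In section 4.2.2, name these items among the end-of-study assessments. CLDQ may be added, but it is exploratory and optional.
3. Reconcile Table 12-2 footnote f with section 6.4.8, so that PT/INR is drawn wherever either score is calculated.
4. Add a line to SAP 8.2.1 saying how a subject who still has no exit score is classified.

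The cost is text and table edits plus, for early leavers only, a small blood sample, a score calculation and, if wanted, a questionnaire. Completers do not need the scores repeated at 14 to 28 days, since Visit 26 provides them about two to four weeks earlier.

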### 3.1.1 Rationale of Study Design

Nonalcoholic steatohepatitis is a chronic inflammatory disease of the liver characterized by progressive fibrosis that eventually leads to cirrhosis in a subset of subjects. Cirrhosis results in portal hypertension, the complications of which (variceal hemorrhage, ascites with bacterial peritonitis, hepatic encephalopathy) can result in death or the need for liver transplantation. There are currently no medical therapies approved for NASH or for portal hypertension by reducing liver fibrosis, and this therapeutic area represents an area of significant unmet medical need. Galectin-3, a protein that binds to galactose-containing oligosaccharides, has been shown to be critical in the pathophysiology of NASH and liver fibrosis. GR-MD-02, a complex carbohydrate drug that binds to galectin-3, has shown robust

efficacy in preclinical models of NASH and liver fibrosis and was safe and well tolerated in Phase 1 studies. Therefore, the overall objective of this clinical study is to establish the safety and efficacy of GR-MD-02 as compared to placebo in the reduction of portal pressure as a surrogate for a reduction in fibrosis in subjects with compensated cirrhosis due to NASH.

Two doses of GR-MD-02 will be evaluated in this clinical study, 2 mg/kg and 8 mg/kg lean body weight. The doses are calculated on lean body weight because the drug is distributed primarily in the blood compartment. These 2 doses were chosen because the drug exposure in humans based on area under the concentration-time curve spans the predicted therapeutic range determined in preclinical studies. The dose of 2 mg/kg is lower than the lowest effective dose evaluated in the preclinical NASH model and 8 mg/kg is in the upper range of the therapeutic window.

GR-MD-02 will be administered every other week over 52 weeks for a total of 26 doses. Liver fibrosis is a chronic condition and, even with an effective therapy, it is likely to require a relatively prolonged therapy to have a clinically relevant effect. Most authorities in the field believe and the US Food and Drug Administration (FDA) advised that 12 months of therapy is likely a minimum required to demonstrate a significant antifibrotic effect.

GR-MD-02 will be compared to a placebo infusion consisting of vials of placebo (phosphate-buffered saline) diluted in 100 mL of normal saline in this study. No therapies have been shown to be effective for the treatment of liver fibrosis in humans and, therefore, placebo is an appropriate comparator.

